## **10 STUDY INTAKE RATE; SAMPLE SIZE PER CLINIC; ENROLLMENT PERIOD**

In order to allow for the possibility of analysis at the individual clinic level, it is desirable that each participating clinic enrolls at least 100 subjects. (However, if more than 8 sites volunteer to participate, fewer subjects per site would be acceptable.)

The rate of intake into the study has implications for the study enrollment period and for workload management. If subjects are enrolled into the 12 week study at a rate of 2 per week, RA's will eventually be managing a study "workload" of 24 subjects and it will take approximately 1 year to enroll 100 subjects. At an intake rate of 3 clients per week, the study workload will be 36 clients and 144 study clients could be enrolled in one year. At an intake rate of 4 per week, the workload would be 48 and nearly 200 subjects could be enrolled in one year.

A one-year enrollment period seems reasonable, with sample size per clinic determined by subject availability. Projected enrollment at each clinic is 100 subjects.

## **11 STUDY PROCEDURES**

## **11.1 Timeline**

A time and events schedule of study activities is shown in Table 1. An outline of the study timeline follows:

1. Determination of study eligibility and randomization
2. Study intervention: 12 weeks
3. Follow-up evaluation: 1, 3 and 6 months after study intake.

**Table 1. Motivational Incentives Time and Events Schedule**

Activity	Screening	Enrollment	Treatment (week)												Follow-up (months)
			1	2	3	4	5	6	7	8	9	10	11	12	
Standard treatment 															
Informed consent	X														
Urine test (test-cup)	X	X	2X	2X	2X	2X	2X	2X	2X	2X	2X	2X	2X	2X	
Alcohol Breathalyzer		X	2X	2X	2X	2X	2X	2X	2X	2X	2X	2X	2X	2X	X
Incentive Drawing		X	2X	2X	2X	2X	2X	2X	2X	2X	2X	2X	2X	2X	
Usual care urine testing 		X		X		X		X		X		X		X	X
Drug-use 	X	X				X								X	X
BSI		X				X								X	X
HIV risk exposure		X				X								X	X
Gambling behavior		X				X								X	X
Employment status 		X				X								X	X
Criminal activity 		X				X								X	X
HIV status		X													
Demographics; DSMIV checklist		X													
Contact information		X													
Treatment history		X												X	X
Counseling utilization 															
Follow-up urine testing						X								X	X

1. Occurs during the entire 12-week study.

2. Performed on alternative weeks during the treatment. May be started in week 2 and performed in weeks 4, 6, 8, 10, and 12.

3. Documented throughout the treatment according to participation.

4. From ASI at enrollment and follow-up CRF at other time-points

## 11.2 Study intake procedures for methadone clinics

Methadone clients will not begin the study until week 5 of treatment or later. It is anticipated that regular (at least biweekly) urinalysis results will be available during this time. Those eligible for the study will have at least one cocaine or methamphetamine positive urine documented during the two weeks prior to study intake.

Clients are approached for study intake by RA's or counselor. The study opportunity will be described to eligible enrollees. Those interested in participation will be escorted to the study intake site. RA or designated counselor will perform the following procedures:

1. Describe study
2. Obtain informed consent
3. Conduct common assessment intake battery (see section 14)
4. Conduct stratification

Subjects will be stratified on two variables prior to random assignment:

- a) presence versus absence of any target stimulant drug in urine
- b) presence versus absence of bonus drug (opiate) in urine.

5. Conduct randomization

Randomization will take place at each site independent of other sites. Thus, stratification by site is not necessary. Stratification and random assignment will be computerized using the dynamic balanced randomization procedure (Signorini et al., 1993).

6. Conduct incentive procedure for those clients assigned to incentive condition who test drug-negative at intake. Remind these clients when they will be eligible for their next recovery pick
7. Discuss urine results in relation to study procedures:

Those in incentive condition testing drug negative will be encouraged to remain negative and reminded of the subsequent recovery pick opportunities.

Those in incentive condition testing drug positive will be encouraged to stop using so they can earn recovery picks as soon as possible and reminded that they can begin earning picks the next time they come into the clinic.

Those in no incentive condition will be encouraged to become or remain drug-free in order to take full advantage of their time in treatment .

8. Allow clients to choose one large incentive for intake bonus.
9. Initiate caserecord for new participant; enter intake data

Whenever possible, all procedures will be completed on the day the client is approached about study participation. If necessary, clients can return the following day to finish intake. In this case, another urine will be collected for use as the first study urine, and this will be counted as the study intake day.

### **11.3 Study drop-out criteria**

Clients will be considered active in the study throughout the three months following study intake independent of clinic attendance frequency, provided they remain enrolled at that clinic. Subjects assigned to the incentive condition are eligible for incentive procedures whenever they come in to the clinic so long as they are currently enrolled for treatment in that clinic. Thus, clients may come to the clinic to leave a urine and participate in incentives even if they do not participate in counseling. Research staff will make every reasonable attempt to notify counselors that a particular client who they want to see has come in.

Clients who have been discharged or terminated from treatment cannot participate in incentive procedures. A uniform drop-out criteria will be adopted by participating clinics. It is anticipated that this criteria will be no face-to-face contact for 30 days (subject to approval by CTP's).

### **11.4 Sample collection and testing procedures**

#### ***On-site urine testing***

Study participants will be expected to give urines twice weekly throughout the 12-week study (total of 24 urines including intake urine). It is recommended that the first urine be collected on Monday and the second on Thursday.

Clients who are absent on the day of scheduled urine collection can give a sample the next time they come to the clinic. Any two samples given within a week on non-consecutive days will qualify for participation in incentive procedures. Special arrangements for urine collection on unscheduled days can be arranged for individuals who have excused absences or emergencies.

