### **16.1 Primary during-study outcomes**

Because the intervention targets stimulant drug use, the most sensitive measures for detecting intervention effects are likely to be measures of stimulant drug use observed during treatment. Therefore, two primary outcome measures will be defined:

- a) Percent of submitted urines cocaine, amphetamine and methamphetamine-free
- b) Longest duration of abstinence from primary target drugs (cocaine, amphetamine, methamphetamine, alcohol)

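### The pre-randomisation intake urine is counted among the 24 study urines, which on the natural reading dilutes percent stimulant-free urines; Table 1 adds to 25

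*Protocol*

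**What the plan says.** Four places in the protocol bear on this.

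- **Section 11.4, on-site urine testing:** "Study participants will be expected to give urines twice weekly throughout the 12-week study", with the bracketed count "total of 24 urines including intake urine".
- **Section 11.2, intake steps:** "Subjects will be stratified on two variables prior to random assignment". The first of these is "presence versus absence of any target stimulant drug in urine". Stratification is step 4 and randomisation is step 5. If intake runs into a second day, "another urine will be collected for use as the first study urine, and this will be counted as the study intake day".
- **Table 1:** the row that begins "Urine test (test-cup" has one mark at screening, one at enrollment and two in every week from 1 to 12. The "Incentive Drawing" row has one mark at enrollment and the same two per week.
- **Section 16.1:** primary outcome (a) is "Percent of submitted urines cocaine, amphetamine and methamphetamine-free". Primary outcome (b) is the longest abstinence from the primary target drugs. The section describes both as drug use seen during treatment. It does not say whether the intake urine is in or out.

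**The concern.** The intervention cannot have affected a urine that was used to stratify before assignment. If that urine is also one of the samples making up the outcome, a baseline value with the same expectation in both arms is averaged into the result and pulls the arms together. Outcome (a) is a percentage of submitted urines, so the weight of the intake sample grows as attendance falls. A participant who never returns would be scored 0% or 100% on a pre-treatment sample alone.

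The count matters as well. Section 11.4 implies 23 scheduled urines after randomisation and Table 1 implies 24. That number is the denominator for the percent-of-expected version of the first primary hypothesis (17.1) and for the percentage of scheduled urines submitted (16.2). The protocol fixes the number itself, in two different ways, so this is not detail left for an analysis plan.

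**Working it through.** **Count.** Section 11.4: 2 × 12 = 24 with intake included, so 24 − 1 = 23 after randomisation. Table 1: 1 + 2 × 12 = 25 from enrollment, or 26 with screening, so 24 after enrollment.

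**Planning figures.** Section 9 gives effect sizes of .16 to .19, mean .18, and 110 to 153 subjects, with two-sided alpha 0.05 and power 0.80. It does not name the effect-size measure. Read as Cohen's f, d = 2f, and n per group = 2(1.96 + 0.84)²/d²:

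- f = .16, d = .32: n = 154
- f = .18, d = .36: n = 122
- f = .19, d = .38: n = 109

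This matches the stated range to within one subject, so d = .32 to .38 is used below.

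**Dilution of outcome (a).** For m submitted urines including intake, with m the same in both arms, the expected difference is Δ × (m − 1)/m. Section 9 gives 28.5% versus 16.3%, so Δ = 12.2 points. Power at 200 per group is Φ(10·d·(m − 1)/m ÷ k − 1.96), since √(200/2) = 10. Here k = 1, or k = 1.2 for the protocol's own 20% allowance for multi-site variability. The SD is otherwise held fixed.

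| Urines per participant, m | Shrinkage | 12.2 points becomes | Power, k = 1 | Power, k = 1.2 |
|---|---|---|---|---|
| intake left out | 0 | 12.2 | 89.3–96.7% | 76.0–88.6% |
| 24 | 4.2% | 11.7 | 86.6–95.4% | 72.4–85.9% |
| 12 | 8.3% | 11.2 | 83.5–93.6% | 68.6–82.7% |
| 6 | 16.7% | 10.2 | 76.0–88.6% | 60.3–75.1% |

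The rows for 12 and 6 suppose that every participant submits that many. In sample-size terms the factor is (m/(m − 1))², that is 1.09, 1.19 and 1.44. The 130 per group quoted in section 9 would become 142, 155 and 188. (That 130 corresponds to an SD of about 35 points, which is back-calculated because the protocol gives none.)

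**Drop-out.** The protocol gives no attendance figures, so this is illustration only. A simulation assumed beta-distributed abstinence rates with means 25% versus 37% or 35% versus 47%, 5% drop-out per visit, and at least one post-randomisation urine each (about 14 on average). The difference in (a) fell by about 12%, for example from 11.9 to 10.5 points. Power at 200 per group fell by about 1 to 9 points, depending on the assumed spread between participants.

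**Outcome (b).** In the same simulations, with and without drop-out, adding the intake urine to 23 later urines did not reduce the raw difference in longest run. With full attendance in one case it was 2.11 tests without intake and 2.16 with it. The standardised effect fell by 0.6% to 1.6% and power by 0.3 to 1.3 points. What remains open is the rule. Section 16.5 scores a single missed test as negative when both neighbours are negative. A missed first post-randomisation test is therefore scored differently according to whether the intake urine counts as a neighbour.

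**The case against.** The strongest reply is that sections 11.2 and 11.4 describe collection and incentive procedures, not outcomes, and that 16.1 speaks of drug use during treatment. The wording about a first study urine covers only the two-day intake. Its purpose may be operational, since an intake negative earns picks. This stands in part: inclusion is inferred, not stated. But 11.4 counts the intake urine among the study urines for everyone, and 16.1 takes submitted urines without exception, so a programmer following the text would include it.

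The 24 and 25 may differ only through layout, if the enrollment cup is the first of the two week-1 urines. That would make 11.4 consistent with itself, but Table 1 does not say so.

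Scoring a participant on a single sample is a consequence of the submitted-urine denominator, and one post-randomisation urine would do the same. That is correct. What is particular to the intake urine is that the single value could predate treatment altogether.

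A reader might infer three stronger things:

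- **That both primary outcomes are diluted.** The check on (b) does not support this.
- **That the result is biased towards one arm.** The intake stimulant result is a stratification factor and so is balanced by design.
- **That power drops below the planned 80%, to about 70%.** That follows only from starting at exactly 80%. At the planned 200 per group the starting point on the protocol's own effect sizes is 89.3–96.7%. With 20% extra variability the lower end is already 76.0% before any dilution.

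**Conclusion.** The point holds for the count and for outcome (a). The protocol gives two incompatible totals, 24 and 25. On its natural reading it also places a pre-randomisation sample in the first primary outcome. The certain part of the loss is small: 4.2% of the effect for a full attender, or about 1 to 4 points of power at 200 per group across both variability settings. It grows as attendance falls, by an amount that the protocol's figures cannot settle.

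This rests on four assumptions:

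- 16.1 is read as including the intake urine.
- The published effect sizes are Cohen's f.
- The SD is unchanged by including the extra sample.
- The arms submit similar numbers of urines. If they did not, the intake sample would carry a different weight in each arm. The protocol gives no attendance figures from which to size that.

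Outcome (b) needs its starting point defined, but its result is hardly affected.

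**What to change.** 1. In 16.1, state that during-treatment outcomes use only urines collected after randomisation. For longest abstinence, this should also say that the intake urine neither opens a run nor serves as a neighbouring test under 16.5.
2. Name the intake urine result, already a stratification factor, as a covariate. The rule in 16.5 adds covariates only after a significant baseline difference, so it is unlikely to bring in a factor that is balanced by design.
3. Give the same number of scheduled post-randomisation urines, 23 or 24, in 11.4 and Table 1, and use it as the denominator for the expected-urine and scheduled-urine percentages. Reconcile the drawing row of Table 1 with the same count. Whether an intake sample earns picks need not change.
4. State how participants with no post-randomisation urine are handled. Under item 1 they have no value on the submitted-urine measure, which is the one real cost in a trial that follows an intent-to-treat sample. The percent-of-expected version in 17.1 gives them a value.

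The cost is a few sentences and one or two table rows. No new data are needed.

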#### ***Sample validity***

It is recommended that all urine collections be observed by a same-sex observer. However, it is recognized that this will not always be possible. The test cups to be used for urine testing have temperature strips included. Criteria for a valid urine will be indicated by the

temperature strip (e.g. above 92 and below 98 degrees Fahrenheit). A further validity check will be provided by Adultacheck, a commercially available test strip that indicates normal ranges for creatinine, pH, gluteraldehyde and nitrates.

Participants whose urine does not pass validity checks will need to give a second sample, if they wish. Otherwise, the sample will be counted as missing (and positive for purposes of incentive procedures).

### ***Testing methods***

Urine testing methods will be uniform across clinics, as specified by the protocol. A 5-panel test cup will be utilized. The drug panel includes cocaine, amphetamine, methamphetamine, morphine and marijuana (THC). Purchase of urine testing supplies will most likely be responsibility of Node study coordinators under pricing structure negotiated by the CTN. Aside from incentive procedures, no clinical decisions will be based on these test results.

### ***Breathalyzer testing***

Breathalyzer testing will be performed at each study visit. If the clinic owns a breathalyzer and routinely conducts testing, this equipment may be utilized. In most cases, a new breathalyzer will be purchased as part of research support. Those qualifying for incentive must read 0.00.

## **11.5 Variable ratio incentive procedures**

Clients randomly assigned to the incentive condition will be able to participate in an incentive procedure each time they test negative for cocaine, amphetamine, methamphetamine and alcohol. Two methods are described below- an abstinence bowl and a computer-based incentive award procedure. It is preferable for all study clinics to use the same method. Therefore it is anticipated that . It is preferable for all study clinics to use the same method. Therefore it is anticipated that a choice will be made prior to protocol implementation of one method or the other after discussion with participating CTP's.

The primary advantage of the computer-based method is that it may reduce the association between abstinence incentive procedures and other gambling behaviors in which clients may participate. Another advantage is that it should reduce the "carnival" atmosphere that has been a focus of objection by some nodes. A third significant advantage is that use of the computer simplifies protocol implementation and avoids any potential problems with client manipulation or tampering.

The primary advantage of the abstinence bowl method is that it minimizes distrust on the part of the participant since s/he directly participates in determining outcome of the incentive procedure. A second advantage is that it may facilitate a positive celebratory atmosphere surrounding the otherwise grim and difficult process of drug abuse recovery.

### ***Characteristics of the abstinence bowl***

Node study coordinators will be responsible for purchasing appropriate vessels for recovery picks. These can be any glass or plastic container of suitable dimensions.

### ***Contents of the abstinence bowl***

CTN will supply coded chits for use in recovery picks. There will be 500 chits supplied for the abstinence bowl. Fifty percent of the chits will say “good job” and will not result in an incentive award. 41.8% of the chits will result in a small incentive, 8% will result in a large incentive and only a very small percentage (0.2%) will result in a jumbo incentive. Chits should be placed on a table in the sequence drawn and remain there until all recovery picks are completed and data has been entered. Chit replacements can be obtained from national study coordinator should any be lost or damaged.

### ***Security of the abstinence bowl***

To prevent tampering, the bowl should be kept in a locked cabinet along with the tangible incentives overnight and whenever it is not in use.

Study coordinator should inventory chits once per month to ensure the proper number, probability distribution and coding.

### ***Recovery pick methods***

Study subjects should pick a chit from the bowl the appropriate number of times for each drug-free urine submitted. A computer program supplied by CTN will assist staff in determining the correct number of recovery picks based on history of drug-free tests. Whenever possible, these recovery pick events should take place in the presence of the study client’s counselor. RA or designated counselor is responsible for recording the results of the pick procedure, for delivering the appropriate incentive and for recording the incentive(s) selected. Clients initial or sign for each incentive received.

### ***Computer-based incentive method***

For this option, the data management software will be programmed to simulate the incentive probability schedule utilized for the abstinence bowl. Thus, client will press a button the appropriate number of times, as calculated on the basis of urine testing history, and the computer will determine (using random probability schedules) and show results of each simulated recovery pick opportunity.

### ***Escalating Schedule of recovery picks for primary drug abstinence***

Clients in the incentive group will earn at least one recovery pick for each sample submitted that tests negative for the primary drugs: cocaine, amphetamine, methamphetamine and provided a negative breath alcohol reading is obtained. The number of picks allowed at each

urine collection will escalate with consecutive week of negative testing on primary drugs. Specifically, an additional recovery pick is added for each consecutive week that the participant tests negative for cocaine, amphetamine, methamphetamine and alcohol.

Study week	Number of recovery picks for primary drug abstinence
1	1
2	2
3	3
4	4
5	5
etc	

Missing or positive samples result in reset to 1 in number of recovery picks for the next negative sample submitted.

The escalating schedule is designed to sustain long periods of abstinence, and as such, the highest rates of reinforcement are scheduled late in the protocol for continuously abstinent participants. In order to counteract discouragement from the low reinforcement rate expected early in the escalating draw protocol, a single \$20 bonus incentive will be given after two consecutive weeks of abstinence from primary target drugs. This bonus incentive can only be received once during the study; if a client re-sets and starts the escalating schedule over again, no bonus incentive will be available.

### ***Bonuses for drug-free panel - opiates.***

Bonus recovery picks will be available at each testing opportunity. This is in addition to the escalating number of recovery picks for the primary drugs described above. As previously described, the bonus pick is based on opiates for methadone maintained participants. Participants can earn two bonus picks for each urine free of bonus target drug (opiates). To earn a bonus pick, clients must also test negative for all of the primary target drugs (cocaine, amphetamine, methamphetamine and alcohol) that day.

### ***Storage and display of tangible incentive***

Tangible incentives will be stored in a durable locking cabinet. Size of the cabinet should be suitable to display items listed below. CTN will provide information about cabinet options; these will be purchased by node coordinators. RA or designated counselor(s) is responsible for keeping cabinet full, keeping inventory of contents, tracking expenditures and incentive awards to individual clients. and soliciting suggestions from clients and counselors on cabinet contents.

### ***Suggested content of tangible incentives- number, type***

The tangible incentives represent part of the active ingredient of this intervention, and thus need to be defined in the protocol. However, CTP's also have latitude in selecting specific

incentives to offer. Guidelines are given below as to the value and content of small, large and jumbo incentive categories. Each study site will be expected to keep an inventory of their incentive stock and incentive awards; this inventory will be facilitated by a computer software program that will be linked to protocol management software.

Jumbo incentive items (average \$80 value)

Generally consist of electronic goods, small appliances or larger valued gift certificates to desirable restaurants, grocery stores and retail outlets. 2-3 jumbo prizes should be on display at all times.

Large incentive items (average \$20 value)

Generally consist of watches, walkmans, gift certificates to a variety of local restaurants and retail stores, clothing items, an AA Blue Book, etc. 10-15 should be on display at all times.

Small incentive items (average \$1 value)

Generally consists of bus passes, candy bars, food items, sodas, toiletries and gift certificates to food outlets (Dunkin Donuts, McDonalds, Subway). 75 should be available at all times. . It is also recommended that some incentives with \$5 value be stocked and that clients who receive multiple \$1 awards be allowed to take a \$5 prize in exchange.

